fNIRS. The human brain is continuously provided with oxygen to ensure normal brain functioning. If a brain area is involved in the processing of a stimulus, it will increase its oxygen consumption as the corresponding neurons will have a higher energy metabolism rate (Allaman & Magistretti, 2013). Higher oxygen demand is first followed by a decrease of oxygenated (HbO₂) and an increase of deoxygenated blood (HbR) in the activated area. To ensure normal functioning, more oxygen will be transported to this area via delayed increased cerebral blood flow. Then, the ratio of HbO₂ to HbR will change again (de Roever et al., 2018). This typical haemodynamic response can be measured with fNIRS because HbO₂ and HbR have different absorption characteristics of the near-infrared wavelengths (Chance et al., 1998; Villringer & Chance, 1997). fNIRS is a safe, non-invasive method which uses these different absorption characteristics to localize brain activity. First, near-infrared light is emitted by a diode to pass through the skull, scalp, and meninges until it reaches the grey matter and corresponding blood vessels. Then, HbO₂ and HbR blood cells partly absorb the light, and the reflected wavelengths are finally detected by a photodetector (de Roever et al., 2018). In sum,

the signal provides an indirect measure of cortical activity which is limited by the time of the haemodynamic response. Although fNIRS has poorer spatial resolution than fMRI and is limited to two-dimensional images of up to 5 cm thickness (Araki & Nashimoto, 1992), it is widely used in clinical and scientific settings with adults, children and even neonates (for reviews, see Ferrari & Quaresima, 2012; Peng & Hou, 2021). To date, no one has used fNIRS to measure foetal brain activity, but previous studies with neonates and especially with preterm infants show its value by accessing the haemodynamic response to increased neural activity in the immature brain (for review, see Peng & Hou, 2021). Furthermore, fNIRS has several advantages compared to fMRI which has been used in previous foetal music perception studies (for review, see Chorna et al., 2019). The stimuli presentation is neither limited by the magnetic field nor by the scanner noise and the pregnant women must not lie in the scanner (Bunce et al., 2006). Therefore, changes in foetal brain activity in response to musical stimulation in studies 2a and 2b will be measured with fNIRS.

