This will be the first study using this neuroimaging method to investigate foetal musical timbre and chord processing on a cortical level. Prior studies have shown that at 34 WG, the foetal head is within 5 cm of maternal external skin (Reid et al, 2017; Donovan et al., 2020). FNIRS is therefore technically feasible for the acquisition of foetal brain function. Using this state-of-the-art technique to investigate foetal brain activity will not only expand the knowledge of foetal music perception, but it might also be groundbreaking for future foetal perception studies in general, as well as possibly offering a non-invasive method for intrauterine clinical assessments.

5. Study procedure

Participation in one of the studies includes providing demographic information as well as attending one experimental session at the Women's Health Clinic, [name], Waikato Hospital. The experimental session will take approximately 45-60 minutes. This includes informed consent, foetal check-ups via 2D-ultrasound, explanations of the procedure, time for questions, the experimental parts (either 1a & 1b or 2a & 2b), a short break in between them as well as a debriefing at the end of the session.

Prior to participation. Every participant will be sent the informed consent sheet (appendix B) and the demographic questionnaire (appendix C) in advance to the session at Waikato Hospital. This allows the mothers-to-be to review the information, to discuss the studies with their family and friends, to take notes regarding any questions or concerns, and to contact the research team if necessary. The criteria for taking part in the studies and their rationales are

clearly outlined in the information sheet and will be discussed with each woman prior to participation.

Every woman will be given a detailed map with instructions where to park and how to get to the entry of the Waikato Hospital Emergency Department where one member of the research team will wait to bring the mother-to-be to the study room. Every woman will get a call or a text the day before her scan to remind her of her appointment on the next day. Contact details of the research team will be provided on the informed consent sheet in case there are any questions or concerns about participation, if the woman cannot make it to the session, or has troubles finding her way to the meeting point.

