welcomed to ask any questions. Afterwards, the experimental procedure will be explained in more detail and exemplary stimuli will be played to give the mothers-to-be an idea of what their babies will hear during the experiments. Each participant will be explicitly asked if she has any questions or concerns, and each will be reminded that the procedure can be stopped in case she feels uncomfortable or wants to withdraw. Neither of them must be justified. Afterwards, the mother-to-be will be asked if she agrees to proceed with the procedure. If she does, she will be reminded to remain silent during the experiments and to lie as still as possible to ensure a high quality of the collected data throughout the experimental parts. Next, the research team will identify foetal position as well as foetal behavioural state (after Nijhuis et al., 1982) using 2D-ultrasound. For studies 1a and 1b, the cardiotocograph (Huntleigh Sonicaid Team3) and the loudspeaker (Marshall Acton III Bluetooth Speaker) will be set-up afterwards and the participant and her whānau or friends will be given headphones before the experiments will start. To access fronto-temporal brain activity in studies 2a and 2b a particular position of the foetus will be required. As previously described, the near-infrared light of fNIRS penetrates up to 5 cm into the maternal abdomen (Araki & Nashimoto, 1992) and if the foetal head is not within this range, the participant will be asked to be taken for a short walk or to drink a glass of water to stimulate foetal repositioning. Otherwise, the experimental procedure cannot be continued, and the women will be asked to return a few days later if she is still interested in participating. If the foetus is in an appropriate position, the fNIRS probe and the loudspeaker will be put into place, headphones will be given to the mother-to-be and her company and the experiments will start.

Each session will include one timbre (studies 1a & 2a) and one chord experiment (studies 1b & 2b) which are separated by a short break in between. The specific structure of each experiment is outlined further below (paragraphs 6 & 7).

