- age-appropriate foetal development: abdominal circumference > 5th percentile, estimated foetal weight \geq 10th percentile, and single deepest pocket \geq 2 cm (Ministry of Health, 2019)
- foetal HR is within the normal range: 120-160 bpm (Von Steinburg et al., 2013)

Exclusion criteria. Consequently, women will be excluded if they meet one or more of the following exclusion criteria:

- multifetal pregnancy
- gestational age is < 35 weeks or >37 weeks
- pregnancy complications which affect foetal HR, auditory, neuronal, or general foetal development
- maternal health issues which put either the mother-to-be or the foetus at risk or which affect foetal cardiac, auditory, neuronal, or its general development
- foetal abnormalities or health issues which affect foetal HR, auditory, neuronal, or its general development (e. g. Down syndrome)
- the foetus is small for gestational age: abdominal circumference < 5th percentile, estimated foetal weight < 10th percentile, and single deepest pocket < 2 cm (Ministry of Health, 2019)
- the foetal HR is not within the normal range: <120/ >160 bpm (Von Steinburg et al., 2013)

Because the near-infrared light only penetrates up to 5 cm into the maternal abdomen (Araki & Nashimoto, 1992), one further exclusion criteria will be applied for the fNIRS studies:

- Women will be excluded if maternal tissue thickness is > 5 cm.

Women of all ethnicities are welcome to take part in the study, ethnicity is not a criterion for participant selection.

10. Participant recruiting

We will actively cooperate with maternal health care providers and maternal health researchers to promote the present research project and to encourage pregnant women to participate in our studies. This includes, but not limits to, Hāpu Wānanga and Te Aukume a Hineteiwaiwa. Furthermore, already established contacts with midwives and birth centres will be used for participant recruitment as well as there will be a media campaign on social media

which was very successful in a previous study (Leov et al., 2023). Finally, all participants will be asked to promote the project in their whānau and to pregnant friends.

11. Remuneration/ koha

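### The fNIRS depth checks stop at maternal tissue and the foetal head, so a session can be accepted with the cortex beyond the protocol's own 5 cm light reach

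*Protocol*

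**What the plan says.** Four parts of the protocol bear on depth.

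- **Reach of the light.** Section 5 (Experimental session) says that "the near-infrared light of fNIRS penetrates up to 5 cm into the maternal abdomen". Section 9 gives the same limit as the reason for its extra fNIRS criterion: "Because the near-infrared light only penetrates up to 5 cm into the maternal abdomen".
- **Enrolment exclusion.** Section 9: "Women will be excluded if maternal tissue thickness is > 5 cm".
- **Session check.** Section 5: "if the foetal head is not within this range, the participant will be asked to be taken for a short walk" or to drink water. If that fails, the session does not go ahead and she may come back another day.
- **Target of the measurement.** Section 4 (fNIRS) describes how "near-infrared light is emitted by a diode to pass through the skull, scalp, and meninges until it reaches the grey matter".

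Section 4 argues feasibility from earlier work showing that "at 34 WG, the foetal head is within 5 cm of maternal external skin", and the background of Section 7 repeats the argument. Section 7 (image acquisition) adjusts light strength to the thickness of the maternal tissue and describes a probe with one emitter and one detector. The Section 7 analysis is a one-way repeated ANOVA for each experiment, with sex and foetal state as exploratory moderators.

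**The concern.** The 5 cm figure limits the whole light path from the maternal skin. What must lie within it is the tissue that produces the signal, the foetal cortex. Neither check measures to that tissue. One stops at the mother's own tissue, the other at the foetal head. On the protocol's own description, further layers lie between the head surface and the grey matter.

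The stake is interpretation. Hypothesis 1 of Section 7 asks whether fNIRS can measure foetal brain activity at all, and Section 2 presents the work as a proof of concept. If some accepted sessions have the cortex out of reach and nobody can say which, a null result has two explanations that the data cannot separate: the method does not work in the foetus, or the light did not get there. Hypotheses 2 and 3, on timbre and chord discrimination at cortical level, inherit the same ambiguity.

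**Working it through.** The 5 cm limit comes from a cited source, so it cannot be re-derived from the protocol. It is taken as stated, and the check is one of path length.

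**Inputs**

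- R = 5 cm, reach of the light from maternal skin (Sections 5 and 9).
- m = maternal tissue thickness under the probe. Section 9 accepts m ≤ 5 cm.
- h = distance from maternal skin to the foetal head. Section 5 accepts h ≤ 5 cm.
- t = thickness of foetal scalp, skull and meninges. Section 4 names these layers but gives no thickness; all that is needed is t > 0.

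**Step 1: which check binds.** The head lies behind the maternal tissue, so h ≥ m at the same place. Any session with h ≤ 5 also has m ≤ 5. The head check is the stricter of the two, and a woman who passes Section 9 must still pass it. Whatever gap exists is therefore the one that the head check leaves.

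**Step 2: depth of the cortex.** c = h + t. The light reaches the cortex, on the protocol's limit, only if c ≤ R, that is h ≤ 5 − t.

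**Step 3: the open band.** Sessions with 5 − t < h ≤ 5 pass both checks with c > 5. The band is not empty for any t > 0, so the point needs no outside figure.

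**Step 4: illustration only.** Values of t are assumed here because the protocol gives none:

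| Assumed t (cm) | Lower edge of band, 5 − t (cm) | Head depths accepted with cortex beyond 5 cm |
|---|---|---|
| 0.3 | 5 − 0.3 = 4.7 | above 4.7, up to 5.0 |
| 0.5 | 5 − 0.5 = 4.5 | above 4.5, up to 5.0 |
| 1.0 | 5 − 1.0 = 4.0 | above 4.0, up to 5.0 |
| 1.5 | 5 − 1.5 = 3.5 | above 3.5, up to 5.0 |

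Turning a band into a share of sessions needs the distribution of h among accepted women. The protocol says only that the head is within 5 cm.

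**Step 5: does anything else close the gap?** The light-strength adjustment in Section 7 is tied to maternal tissue and leaves out the foetal layers. The analysis paragraphs of Section 7 do not use depth. No section sets a skin-to-cortex distance.

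**Step 6: would a depth covariate repair it afterwards?** Write the response of foetus i to stimulus j as Y_ij = μ + s_i + b_j + γd_i, with d_i the depth. The within-foetus contrast is Y_i1 − Y_i2 = b_1 − b_2, and γd_i cancels. A main effect of depth therefore leaves the comparison of interest unchanged. With an interaction δ_j d_i added, the contrast becomes (b_1 − b_2) + (δ_1 − δ_2)d_i and can vary with depth.

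**The case against.** The strongest reply is that the two rules are successive gates and not rival definitions. Maternal tissue thickness cannot be changed by repositioning, so it belongs at enrolment; foetal position can change, so it belongs in the session. This stands. A reader might infer that a woman with, say, 4.8 cm of maternal tissue goes straight into the analysis. The documents do not support that, because she must still pass the head check.

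Second, Section 5 says foetal head, not head surface, and does so while discussing access to the fronto-temporal brain. The surface reading is the natural one, since Sections 4 and 7 speak of the head's distance from the mother's skin, but it is not explicit. That is itself a reason to name the landmark.

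Third, 5 cm may not be a hard wall. Section 4 also describes it as an image thickness, and Section 7 adjusts the light to keep sensitivity consistent. This is fair: the point holds on the protocol's own use of 5 cm as a limit, and does not show that no signal comes from deeper.

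Fourth, a reader might infer that out-of-reach sessions will enter the analysis in some definite proportion and shrink the planned effect of f = .1 by a known amount. That is not supported. Such sessions can enter; whether they do, and how many, depends on depths and layer thicknesses that the protocol does not give. If most heads lie well inside 5 cm, the share could be near zero. Signal-quality rejection may sit in an analysis plan that is not shown, and the 50 % attrition assumed in Section 14 might absorb some sessions. The protocol links neither to depth.

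**Conclusion.** The point holds in a limited form. On the protocol's own statements, a session that meets both depth rules can have its cortex beyond the stated reach of the light, and no other section prevents this. It rests on three things: 5 cm is the total reach from maternal skin, foetal head means its near surface, and the foetal layers have some thickness.

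The number of affected sessions is unknown, and no figure for lost power or a diluted effect is claimed. The consequence is for interpretation: a null on hypothesis 1 would be ambiguous. The correction is worth making before recruitment because it is cheap and a missing distance may not be recoverable later.

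**What to change.** - Keep the maternal tissue exclusion in Section 9 as a first screen.
- Reconcile Sections 4, 5, 7 and 9 on the landmark to which 5 cm applies. In Section 5, apply the protocol's own 5 cm reach to the distance from maternal skin to the inner border of the foetal skull under the probe, read on the 2D-ultrasound already used to place it. This landmark leaves out the meninges and so is still slightly generous; the text should say so.
- Record that distance for every fNIRS session.
- Repeat the fNIRS analyses restricted to sessions with the cortex within reach. If depth is modelled, include its interaction with stimulus, for the reason in Step 6 of the working.

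The cost is a few lines of text and one extra reading in an existing scan. The downside is that somewhat more sessions will be rebooked or not used. Section 5 already provides for a return visit, but the protocol does not allow one to tell whether the attrition allowance in Section 14 would cover the extra losses.

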To date, it is unclear whether foetuses can percept and discriminate different musical timbres and if so when these abilities develop. The same is true for the perception and differentiation of major vs. minor chords. There is a lack of intrauterine music perception studies in general, and foetal discrimination of musical timbres and chords have not yet been studied. The PhD therefore uses cardiotocography (CTG; studies 1a & 1b) and for the first time, functional near-infrared spectroscopy (fNIRS; studies 2a & 2b) to investigate foetal abilities to percept and differentiate musical timbres as well as major from minor chords. Foetal brain activity during musical stimulation will be measured with fNIRS which will act as a proof of concept for foetal brain imaging in addition to giving a better understanding of the development of music processing during the foetal period.

The PhD has the following research questions:

1. Do foetuses at 35-36 weeks GA habituate to auditory stimuli over the course of multiple trials?

2. Can foetuses at 35-36 weeks GA discriminate between different timbres?
3. Do foetuses show differentiable HR responses between major vs. minor chords at 35-36 weeks GA?
4. Is it possible to investigate foetal brain activity with fNIRS?
5. Are foetal discriminatory abilities for timbres and chords present at a cortical level at 35-36 weeks GA?

3. General

Each of the four studies of the PhD will use an experimental, cross-sectional, within-subjects design. Foetal HR will be collected in studies 1a (timbre) and 1b (chord) as it has proven its reliability in previous foetal music perception studies (e. g. Kisilevsky et al., 2004; Lecanuet et al., 2000; Tristao et al., 2020). In addition, foetal brain activity will be measured using fNIRS in studies 2a and 2b to investigate timbre and chord processing on a cortical level. This will be the first study using this state-of-the-art neuroimaging technique to measure foetal brain activity. Introducing fNIRS into foetal research will not only expand the knowledge of foetal music perception, but it might also be groundbreaking for foetal research in general, as well as possibly offering a non-invasive method for intrauterine clinical assessments.

The data collection for all four studies will take approximately 1-1.5 years.

4. Materials and methods

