Background. So far, the discrimination of musical timbres and chords have not been investigated during gestation, but several studies have shown that foetal HR is a valid measure of foetal auditory and music perception abilities. For example, 70 % of the fetuses (36-39 weeks GA) who participated in the study by Lecanuet et al. (1999) showed a HR deceleration after the presentation of a note (D4/ C5), and 90 % of these fetuses responded with another HR deceleration after a second note (C5/ D4) was presented. Furthermore, Kisilevsky et al. (2004) reported an initial HR decrease of fetuses at 35-36 weeks GA in response to a lullaby played at 95 dB. This change in HR peaked approximately 5 seconds past stimulus onset. When the same lullaby was played at higher SPL (100-110 dB), fetuses did not show an initial HR decrease, but responded with a continuous HR acceleration while the lullaby was played for 5 minutes. This finding is in line with other studies which reported a significant HR deceleration to sounds played at lower SPL (e. g. Lecanuet et al., 1988; 1992; 1993), while an increase of the SPL to 100 dB and above typically leads to the occurrence of cardiac accelerations (for review, see Lecanuet & Schaal, 1996). Following the initial HR decrease, fetuses show a continuous HR acceleration during auditory stimulation which slowly returns to baseline after stimulus offset (e. g. Kisilevsky & Hains, 2011; Lee, 2010).

These last studies have investigated foetal voice perception which is especially interesting for the timbre experiments as every voice has a unique timbre. Near-term fetuses (≥ 36 weeks GA) showed discriminatory abilities between a male and a female voice uttering the same sentence which was reflected by an initial HR deceleration that peaked 10-20 seconds after stimulus onset (Lecanuet et al., 1992). Furthermore, the initial HR decrease was followed by a prolonged HR increase in term fetuses (≥ 38 weeks GA) with low vagal tone (Smith et al., 2007).

At the same time, there was no difference in foetal behavioural responses to the maternal voice at 36-38 weeks GA, neither compared to another female's (Hepper et al., 1993; Kisilevsky et al., 2003), nor to the father's voice (Lee, 2010). It was therefore decided to investigate only foetal cardiac responses, and not foetal movements.

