Procedure. After written informed consent and foetal check-ups, the experimental procedure of the two studies will be explained to the participant. Two exemplary trials of each of the two experiments will then be presented. These are a C4 played by a piano for study 1a and one trial each with a F-major and a f-minor chord for study 1b. Both are also played by a piano. After the participant confirms that she has no further questions and agrees to move on to the actual experiments foetal position and behavioural state will then be identified. Baseline 1 will follow and experiment 1a will start thereafter. Each timbre will be presented in three separate blocks of 30 seconds which are separated by 30 seconds of silence to allow the foetal HR to return to (near) baseline levels in between sound blocks (e. g. Morokuma et al., 2008). The sound blocks include six sounds of 3.492 seconds alternated with 1.508 seconds of silence. This design was chosen based on previous studies which showed successful HR responses to auditory stimuli using blocks of sounds with silence and blocks of no sound in between them (Kisilevksy et al., 1989; Lecanuet et al., 2000; Lee, 2010). The timbre experiment will take 9 minutes. Afterwards, a brief break will follow. Next, baseline 2 will start and the chord stimuli will then be presented in three separate blocks for each chord category. Each of the blocks is also 30 seconds, but the sounds are only 1.327 seconds long and separated by 1.673 seconds

of silence which results in 10 sound presentations per block. The shorter sound length is due to the specific temporal characteristic of the instrument used to play these stimuli as tones played by the piano have a very quick attack and a very short release phase (Müller, 2015). The chord experiment is 6 minutes long.

The order of the stimuli in both experiments as well as the order of the experiments themselves will be counterbalanced across participants to control for possible order effects.

Data analyses. Foetal HR will be analysed in two separate two-way repeated analyses of variances (ANOVA) to compare foetal responses to the three different timbres (study 1a) as well as between major and minor chords (study 1b).

Degrees of freedom will be adjusted if the assumption of sphericity is violated in either of the analyses. Post hoc comparisons will be done with Tukey tests ($p < .05$) and Bonferroni-correction will be used for α -adjustment to take multiple comparisons into account.

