As there have not been any previous studies investigating the perception and discrimination of musical timbres and chords in the foetus, there were no previous effect sizes for the estimation of sample size. Therefore, to maximize the probability to find an effect, a conservative, small within factor effect of $f = .1$ was chosen. Based on a probability of $1 - \beta = .95$, an α -value of $\alpha = .05$ and a theoretical correlation of $\rho = .50$ between repeated measurements, a priori calculation using G.Power 3.1.3 (Faul et al., 2009) yielded in a sample size of $N = 84$ for 18 trials per condition for the HR timbre experiment (study 1a). Using the same psychometric input values ($f = .1$, $1 - \beta = .95$, $\alpha = .05$, and $\rho = .50$), a sample size of $N = 60$ was calculated for the HR chord experiment (study 2b) which includes 30 trials per chord category (major vs. minor). Given an attrition rate of approximately 20 % in foetal HR studies (e. g. Lecanuet et al., 1992; Lecanuet et al., 2000) data of 101 participants will be collected for the HR studies.

Using the same psychometric input values ($f = .1$, $\alpha = .05$, $1 - \beta = .95$, and $\rho = .50$), a sample size of $N = 69$ for 24 trials per timbre and $N = 70$ for 24 trials per chord category was calculated for the studies 2a and 2b, respectively. Previous fNIRS studies with newborns reported an

attrition of approximately 40 % (for review, see Lloyd-Fox et al., 2010) while foetal neuroimaging studies sometimes had to exclude 50 % of their participants (e. g. Jardri et al., 2008). Because no one has used fNIRS for foetal research before, sample size estimation will be based on a conservative attrition rate of 50 % and 105 women will be collected for the fNIRS studies.

Please note that the final estimated sample size for both set of studies was oriented on the estimations for the experiment where a larger number of participants was needed to find a small effect of $f = .1$. This was the timbre experiment for the HR studies and the chord experiment for the fNIRS studies.

15. Māori consultation

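### Section 14's 95 % power is for differences among successive single sounds, not for the planned timbre and chord comparisons, and the power of those comparisons cannot be read from the protocol

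*Protocol*

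**What the plan says.** Section 14 (Estimation of sample size) reports that, for lack of earlier effect sizes, "a conservative, small within factor effect of $f = .1$ was chosen". With power .95, α = .05 and a correlation of .50 between repeated measurements, it obtains:

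- N = 84 "for 18 trials per condition for the HR timbre experiment (study 1a");
- N = 60 for the heart-rate (HR) chord experiment, "which includes 30 trials per chord category (major vs. minor"). The text labels it study 2b, but from context it is 1b;
- N = 69 for study 2a and N = 70 for study 2b, each with 24 trials per condition.

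The larger N in each pair sets recruitment: 101 women for the HR studies and 105 for the fNIRS studies.

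Elsewhere the protocol fixes the design and the tests. Section 3: "Each of the four studies of the PhD will use an experimental, cross-sectional, within-subjects design". Sections 6 and 7 name timbre (three levels) and chord category (two levels) as the independent variables. HR is to be analysed by two-way repeated-measures ANOVA and brain activity by one-way repeated-measures ANOVA on timbre or chord. In study 1a, "Each timbre will be presented in three separate blocks of 30 seconds". HR hypotheses 5 and 6 compare the first response to a new stimulus with the last block of the previous one.

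**The concern.** Each N in section 14 is tied to a count of single sounds, whereas the tests compare three timbres or two chord categories within the same foetus. Studies 2a and 2b have the same 24 trials per condition and the same inputs, yet their Ns differ by one (69 and 70). That suggests the number of conditions entered as a number of groups, although the design has none.

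If the sounds were the repeated factor, the calculation answers a different question from the one the trial asks. The stated 95 % could then not be used to plan the discrimination tests, or later to judge what a non-significant result means.

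**Working it through.** **Inputs.** From section 14: f = .1, ρ = .50, α = .05, target power .95, and 18, 30, 24 and 24 trials per condition. The number of groups and the sphericity value are not stated. I take sphericity as met (ε = 1) and infer the groups.

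**Step 1: reproduce the stated Ns.** For the within-factor test with m repeated measurements and k groups:

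λ = f²·N·m/(1 − ρ), df1 = m − 1, df2 = (N − k)(m − 1),

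with power from the noncentral F and N rounded up to a multiple of k. For study 1a, λ = .01 × 84 × 18/.5 = 30.24, with df 17 and 1377.

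| Study | m | k | N | Power | Power one step lower | N if k = 1 |
|---|---|---|---|---|---|---|
| 1a | 18 | 3 | 84 | .957 | .948 (N = 81) | 82 |
| 1b | 30 | 2 | 60 | .953 | .945 (N = 58) | 60 |
| 2a | 24 | 3 | 69 | .953 | .942 (N = 66) | 68 |
| 2b | 24 | 2 | 70 | .957 | .94996 (N = 68) | 68 |

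All four Ns match. With one group, 2a and 2b would share the same N, so the 69 and 70 point to 3 and 2 groups. Other settings fail: the within-between interaction gives 105, 60, 90 and 70, and the between-groups test gives 819, 674, 810 and 680. With one group or with several, df1 is 17, 29, 23 and 23, so the effect powered is a difference among successive sounds.

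**Step 2: the planned comparison, f taken on condition responses.** One group, m = 3 (timbre) or 2 (chord), ρ = .5. For 1a, λ = .01 × 84 × 3/.5 = 5.04, with df 2 and 166.

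| Study | N | Power | N for .95 |
|---|---|---|---|
| 1a | 84 | .50 | 259 |
| 1b | 60 | .33 | 327 |
| 1b | 84 | .44 | 327 |
| 2a | 69 | .42 | 259 |
| 2b | 70 | .38 | 327 |

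**Step 3: f taken at a lower level.** If f applies to a single response, t of these are averaged per condition and all correlations equal .5, then λ = f²·N·m·t/(1 − ρ).

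- Per HR block (t = 3): 1a, λ = 15.12, power .94. 1b, λ = 7.20 at N = 60 and 10.08 at N = 84, power .75 and .88. N for .95 would be 88 (timbre) and 111 (chord).
- Per single sound (t = 18, 30, 24, 24): λ = 90.7 (1a), 72.0 (1b, N = 60), 99.4 (2a) and 67.2 (2b). Power exceeds .99 in all four, and N for .95 would be 16, 13, 13 and 16.

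At ρ = .5, none of the three readings returns the stated Ns.

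**Step 4: the block contrast of HR hypotheses 5 and 6.** One change, last block against first new block, is a two-level comparison. With f = .1 per block and ρ = .5, λ = .01 × 84 × 2/.5 = 3.36, and power at N = 84 is .44.

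**Step 5: sensitivity to ρ.** At the condition level with ρ = .8, power is .89 (1a, N = 84), .82 (1b, N = 84), .82 (2a) and .74 (2b). Over ρ = .3 to .9 the N for .95 runs from 362 to 53 (timbre) and from 457 to 67 (chord).

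**The case against.** The strongest reply is that trials are part of the question. The first research question in section 2 asks about habituation over repeated trials, so for the HR studies a repeated-presentation effect is a stated aim. This does not rescue section 14. HR hypothesis 2 places habituation across blocks, the fNIRS ANOVAs contain no trial factor, and section 14 itself is framed around perception and discrimination of timbres and chords.

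A second reply is that the group setting is inferred. That is true: section 14 does not give it. The inference is strong, but it moves N by at most 2, and the point rests on the repeated factor alone.

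A third reply stands. A reader might infer from the .33 to .50 that the studies are under-powered, and that 259 or 327 foetuses are needed. The documents do not support that, because section 14 does not say to which response f = .1 belongs, and another level or a higher ρ gives adequate power. The high figure is a natural reading for fNIRS, where each sound is a separate trial in what section 7 describes as an event-related measure. It is harder to hold for HR: sounds start every 5 s (timbre) or 3 s (chord), while section 6 cites an "initial HR deceleration that peaked 10-20 seconds after stimulus onset". That figure comes from a voice study, however, and no section states outright that HR is scored per block; this is inferred from the hypotheses.

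Nor does the protocol say that a null result will be taken as absence of discrimination.

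**Conclusion.** The mismatch is established: section 14's 95 % power at f = .1 belongs to a test among 18, 30, 24 or 24 successive sounds. It does not apply to the three-level timbre comparison, the two-level chord comparison, or the block-to-block change in HR hypotheses 5 and 6. The software arithmetic is right; the effect it was applied to is not the planned one.

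The direction and size of the error are not established. At the stated Ns the power of the planned comparison runs from .33 to above .99, according to the level at which f is defined. All figures assume sphericity, and the averaged ones also assume equal correlations. The conclusion is therefore that the claimed power is unsupported for the discrimination tests, not that the trial is too small.

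**What to change.** Rewrite section 14 at the planned N:

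1. Compute for one group with 3 (timbre) or 2 (chord) within-subject levels and, for HR hypotheses 5 and 6, for the block-to-block contrast.
2. State the response to which f and ρ refer (condition mean, block or single sound), and the sphericity and correlation assumptions.
3. Replace the claim of 95 % power at f = .1 with the resulting power or detectable effect. If f is defined on condition responses with ρ = .5, the detectable f at 95 % power is about .18 (1a, N = 84), .20 (1b, N = 84), .20 (2a, N = 69) and .22 (2b, N = 70).

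The cost is the rewriting of one section. No participants are added, and design and analysis are unchanged. The downside is that the stated figure may become less favourable.
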